8 STUDY INTERVENTION DISCONTINUATION AND SUBJECT DISCONTINUATION/WITHDRAWAL

8.1 Criteria for Discontinuation or Withdrawal of a Subject

GDH is a non-significant risk behavioral intervention. Given this, there are no foreseeable safety-related reasons to discontinue the study. Subjects may freely withdraw their individual participation in the study at any time. However, in case there is a reason for discontinuation or withdrawal of the subject from the study this should be recorded in the eCRF using the following categories (for screen failure subjects, refer to [Section 5.4](#)):

1. Treatment discontinuation due to an AE. The subject has experienced an AE that in the opinion of the investigator may expose them to undue risk or could interfere with his/her continued participation in the study.
2. Important protocol deviation. The discovery post randomization that the subject failed to meet protocol entry criteria or did not adhere to protocol requirements, and continued participation poses an unacceptable risk to the subject's health, following consultation with the sponsor or designee.
3. Lost to follow-up. The subject stops responding to requests and reminders for data collection or treatment and attempts to contact the subject were unsuccessful. Attempts to contact the subject must be documented in the subject's electronic source documents.
4. Voluntary withdrawal. The subject (or subject's legally acceptable representative) wishes to withdraw from the study. The reason for withdrawal, if provided, must be recorded in the eCRF. Note: All attempts should be made to determine the underlying reason for the withdrawal and where possible, the primary underlying reason should be recorded (i.e., withdrawal due to an AE should not be recorded in the "voluntary withdrawal" category. Similarly, lack of efficacy should not be recorded in the "voluntary withdrawal" category).
5. Study termination. The sponsor, IRB, or regulatory agency terminates the study.
6. Subject is found to have a life-threatening medical illness or serious mental health disorder
7. Any other clinical event or finding that, in the opinion of the study team, jeopardizes subject safety, privacy, or the scientific validity of the study.

8.2 Procedures for Discontinuation or Withdrawal of a Subject

The investigator may discontinue a subject's study participation at any time during the study when the subject meets the study termination criteria described in [Section 8.1](#). In addition, a subject may discontinue his or her participation without giving a reason at any time during the study. Should a subject's participation be discontinued, the primary criterion for termination must be recorded by the investigator. Subjects withdrawn by the sponsor due to investigator error in applying protocol inclusion/exclusion criteria or technical issues in the Curebase software that

prevent appropriate execution of the trial will be replaced. Otherwise, subjects will not be replaced.

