3. A simple user interface (UI) with an arrow play button that starts the treatment session. (see [Figure 3](#))

In addition to the EAGLEFISH app, subjects enrolled in the EASITx study will be required to enter study data in a second platform. The Curebase platform is for data collection and administers the daily ePRO and provides access to periodic surveys. Subjects will be introduced to the Curebase platform at the baseline screening clinic visit by the research study staff. Study staff will explain the use of the app and the process by which subjects will enter data in the ePRO.

After completion of the 4-week run-in period (Phase 1), subjects will be informed of eligibility, and eligible subjects will be scheduled for a day 0 phone call (scheduled as soon as possible but no more than 14 days from completion of the run-in period). On the day 0 phone call, after a subject is randomized, the Curebase staff will confirm the subject's preferred day of the week, time of day and start date for treatment. Curebase staff will enter the treatment schedule and randomization code (blinded treatment allocation) into a secure metaMe portal that automatically triggers the assigned treatment and the subject-specific treatment reminder and scheduling system. Curebase staff will assist subjects in accessing the metaMe digital platform by guiding them through the process of creating a metaMe login username and password and reviewing the process for accessing the treatment app. Subjects will be guided through the login process and directed to the navigation menu. The navigation menu contains the following items:

1. The home button
2. Account information
3. Treatment schedule
4. Logout
5. Help section. Contains a link to watch or read a transcript to the intro video (see below), FAQ and contact information for technical support and problems with treatment.

[figure not shown]
The treatment process will commence within 7 days of the day 0 call and will be initiated by system-generated text and email reminders of upcoming treatment sessions. Subjects will be sent an email reminder 24 hours and 1 hour before each session, and a text message reminder 5 minutes before each session. Subjects will be able to access the treatment app via a hyperlink in these messages or directly by opening the app on their device. Once in the app, subjects will

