initiate treatment by pressing the large arrow start button on the home screen (see User Guide and [Figure 3](#)). The first thing subjects will see is a short 3-minute intro video that explains the following details of treatment:

1. Treatment session length
2. The treatment reminder system, which uses emails and text messages to alert subjects of upcoming treatment sessions and to remind subjects to complete treatment.
3. The process for rescheduling and managing missed treatment sessions (subjects have 3 additional days to complete the treatment before they are considered a missed treatment)
4. Rules on interrupted treatment sessions (subjects must start over from the beginning and have 3 opportunities to finish the treatment before they are considered a missed treatment)
5. The recommended minimum number of practice sessions is 3 over the 13 days between treatments.

There are two intro videos customized to each of the two treatments. They differ in the treatment-specific instructions; in the case of the GDH treatment, the video has specific instructions on how to manage re-alerting after hypnotherapy (see [Appendix F](#)). In the case of the MR treatment, subjects are given guidance on how to manage muscle-specific complaints (see [Appendix G](#)) After the completion of the treatment session, subjects will be instructed to click a button indicating they have completed the session. This button appears upon completion of 100% of the length of the treatment session. A session is also considered completed if greater than 95% of the video is played and no button is pressed by midnight of that day local time. Subjects who miss their scheduled treatment will have 3 additional days in which to complete the treatment. They will receive daily text and email reminders to complete treatment. If after 3 days the subject has not completed the treatment session they will be locked out of that treatment and it will be scored as a missed treatment session. Similarly, subjects will receive a one-time reminder about Practice sessions on the 5th, 8th, and 11th day after each treatment. Subjects will be allowed to access one practice session per day for as many non-treatment days as they like but they will only receive 3 reminders at the indicated days.

The subject experience with the EAGLEFISH app is illustrated in the User Guide and briefly in [Figure 3](#).

Figure 3 metaMe Treatment Visual Narrative**EAGLEFISH User Interface (UI)**

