8.6 Adverse Events and Serious Adverse Events

8.6.1 Definition of Adverse Events

Adverse event¹ means any untoward medical occurrence, unintended disease or injury, or untoward clinical signs in subjects, whether or not related to the investigational medical device (21 CFR 312.32 (a)).

In the context of the investigational device, an AE constitutes:

- any unintentional, unfavorable clinical sign or symptom, including complications of IBS (but not IBS itself).
- any new illness or disease or the deterioration of existing IBS

¹ ISO14155 and 21 CFR 812

- any clinically significant deterioration in any clinical assessment or outcome measure
- Any adverse event resulting from insufficiencies or inadequacies in the instructions for use, the deployment, the installation, the operation or any malfunction of the investigational medical device. This includes any event that is a result of a use error or intentional abnormal use of the investigational medical device

Pre-existing conditions (unless worsened significantly during treatment) or routine diagnostic and therapeutic procedures normally administered in the treatment of IBS do not constitute AEs. AEs will be collected from the time a subject signs the informed consent until study withdrawal, screen failure, or study completion.

If the subject experiences a worsening or complication of an AE after ongoing treatment, the worsening or complication should be recorded as a new AE. Investigators should ensure that the AE term recorded captures the change in the condition (e.g., “worsening of...”).

In this study, it is possible that some subjects may experience a worsening of IBS symptoms. As the primary endpoint of this study, worsening of IBS symptoms is captured as part of the efficacy parameter. Worsening of IBS symptoms should not be considered an AE unless the worsening of the symptoms is associated with a cause other than the subject’s IBS.

All AEs that occur in study subjects during the AE reporting period specified in the protocol must be reported, WHETHER OR NOT THE EVENT IS CONSIDERED RELATED TO THE STUDY TREATMENT.

NONSERIOUS AEs are to be documented on the AE CRFs.

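### Section 8.2 permits the investigator to end a randomised subject's whole study participation on Section 8.1 criteria, and no section asks for the daily pain diary afterwards

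*Combined protocol and SAP*

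**What the plan says.** Section 8.1 lists seven reasons for discontinuation or withdrawal from the study and says that "this should be recorded in the eCRF using the following categories". Item 1 is headed "Treatment discontinuation due to an AE". Item 2 is an important protocol deviation where continuing poses an unacceptable health risk, after consultation with the sponsor or its designee. Item 6 is life-threatening illness or serious mental health disorder. Item 7 is any other clinical event or finding that, in the study team's opinion, "jeopardizes subject safety, privacy, or the scientific validity of the study". Items 3 to 5 are loss to follow-up, voluntary withdrawal and study termination.

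Section 8.2 then says that the investigator may discontinue a subject's "study participation at any time during the study when the subject meets the study termination criteria" in 8.1. The step it requires afterwards is to record the primary criterion. Two grounds lead to replacement: investigator error in applying the entry criteria, and technical faults in the Curebase software. "Otherwise, subjects will not be replaced".

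Section 8.6.1 states: "AEs will be collected from the time a subject signs the informed consent until study withdrawal, screen failure, or study completion". Section 9.3 keeps all randomised subjects in the ITT population apart from those replaced. Section 9.4.1 requires at least half of the daily assessments in a 4-week period before an average can be derived. It treats missing post-baseline values in two ways, left missing or multiply imputed, and includes whatever data withdrawn subjects have already supplied.

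**The concern.** Stopping treatment and leaving the study are different events, and 8.2 provides one procedure for both. A subject whose treatment is stopped for an adverse event may still be able and willing to score pain each day. If the investigator uses the 8.2 power, that subject's participation ends, and nothing in the protocol asks for further diary entries. The subject stays in the ITT population, but if this happens before enough of Phase 3 has been recorded, responder status cannot be derived. It is then missing in one planned analysis and imputed in the other, although it could have been observed.

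The platform would allow the two to be separated. Treatment is delivered in the EAGLEFISH app, while "The Curebase platform is for data collection and administers the daily ePRO and provides access to periodic surveys". The protocol already keeps subjects who do not take treatment as scheduled: after the grace period for a missed session, "they will be locked out of that treatment and it will be scored as a missed treatment session", and the subject carries on in the study.

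**Working it through.** **1. Does any section require the diary after an investigator-led discontinuation?**
- 8.2: record the criterion; nothing on further data.
- 8.3: contact after missed sessions or data points, for a subject still in the study. Whether the subject continues in the study is treated as one decision.
- 8.6.1: adverse event collection ends at study withdrawal. This supports reading the end of participation as the end of data collection, but it does not mention the diary.
- 8.6.4: adverse events are followed for their outcome; nothing on pain scores.
- 9.4.1: existing data from withdrawn subjects are analysed; no new data are sought.

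None requires it.

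**2. When does discontinuation make the endpoint underivable?** Phase 3 has 28 days, so the threshold is 0.50 × 28 = 14 entries. Treatment lasts 12 × 7 = 84 days. Ending participation on day 97 leaves at most 97 − 84 = 13 Phase 3 entries. Discontinuation on or before day 97 of 112 therefore loses the endpoint even for a perfect diarist. This is calendar arithmetic, not a risk.

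**3. The plan's own power figure.** Inputs from 9.2: 300 completers (150 per arm), comparator 26%, difference 18 points (so GDH 44%), 5% level; 9.1 makes it two-sided. Normal approximation, pooled null variance, mean rate 0.35:

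Power = Φ{[0.18 − 1.96·√(2·0.35·0.65/n)] / √[(0.44·0.56 + 0.26·0.74)/n]}

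At n = 150: (0.18 − 0.1079)/0.0541 = 1.33, giving 90.9%. The stated figure of at least 90% is reproduced.

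**4. Precision cost.** The documents give no count of such discontinuations, so 2, 5 or 10 per arm are assumptions. Start from 380/2 = 190 per arm, no other dropout, and losses unrelated to outcome, so the expected difference stays at 18 points. Unstratified half-width = 1.96·√[(0.44·0.56 + 0.26·0.74)/n]. The power column instead takes the same losses on top of the planned dropout, from 150 per arm.

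| Lost per arm | n for half-width | 95% half-width (points) | n for power | Power |
|---|---|---|---|---|
| 0 | 190 | 9.42 | 150 | 90.9% |
| 2 | 188 | 9.47 | 148 | 90.5% |
| 5 | 185 | 9.55 | 145 | 89.9% |
| 10 | 180 | 9.68 | 140 | 88.9% |

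The plan already allows 380 − 300 = 80 subjects not to complete Phase 3, so these losses may fall inside that allowance and leave the planned power unchanged.

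**The case against.** The strongest case is that this is a rare, discretionary event with almost no effect. Much of that stands.

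- Section 8.2 says the investigator may discontinue participation. A reader might infer that stopping treatment automatically ends follow-up; the text does not say so. Item 1 itself covers adverse events that could interfere with continued participation, so it is not purely a treatment reason.
- A reader might also infer that any of the seven items gives the investigator a free hand. Items 3 to 5 are not investigator choices, item 2 needs a health risk and sponsor consultation, and missed sessions are not a listed ground. Only items 1, 2, 6 and 7 matter here, and in some of those cases safety or privacy would properly end data collection too.
- Cases are likely to be few. Section 8.1 foresees no safety-related reason to discontinue the study. Section 3.3.1 reports under 1% non-serious treatment-related adverse events in reviewed hypnotherapy trials with similar exclusions, and no treatment-related events among 300 subjects allocated to therapist-delivered GDH. These figures do not count withdrawals for all causes or describe the comparator, but they point to the low end of the table.
- The protocol defers further missing-data detail to the SAP, and that text was not available for this point. It could change how a missing outcome is analysed. It would not normally collect the outcome.

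What remains is that discretion is given with no default in favour of keeping the diary.

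**Conclusion.** The point holds as a modest, inexpensive improvement to data collection. Following 8.2 as written can lose the primary outcome of an ITT subject who was still able to report it. The number of such cases is unknown and probably small. With an assumed 2 per arm, unrelated to outcome, the half-width widens by 9.47 − 9.42 = 0.05 points.

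A reader might infer that the primary comparison is biased. The documents do not support that: Section 7.2.1 keeps investigators unaware of assignment, and nothing shows that removals would differ by arm or by outcome. Larger shifts need assumptions the plan does not make. For example, if 5 subjects were removed from one arm only and all were responders, the difference would move by −1.5 points (GDH: 83.6 − 5 = 78.6; 78.6/185 = 42.5% against 44%) or +2.0 points (comparator: 49.4 − 5 = 44.4; 44.4/185 = 24.0% against 26%). Scoring removed subjects as non-responders is likewise not one of the two approaches in 9.4.1. Nor is this an error in the sample size, which is reproduced and carries an allowance for non-completion.

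**What to change.** Replace the first sentence of 8.2 rather than adding to it, because a new sentence beside the present one would contradict it. Proposed text:

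*The investigator may discontinue a subject's study treatment when the subject meets a criterion in Section 8.1. Unless the subject withdraws consent, or safety or privacy prevents it, the subject will be asked to continue the daily pain diary and scheduled surveys through week 16 and the LTE assessment periods.*

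The long-term extension is included because durability is a secondary objective. Keep 8.1 as the list of recording categories. Leave loss to follow-up, voluntary withdrawal, study termination and the two replacement grounds as they are.

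Cost: one IRB-approved amendment to one sentence. The diary and reminders already exist in Curebase, and Section 6.5 already ties payment to contributing data, so extra reminder and payment costs are minor. There are two downsides. Some ITT data will come from subjects who are off treatment, which may dilute the difference relative to an on-treatment comparison. The daily entry burden, which Section 3.3.3 acknowledges, continues for a subject who has stopped treatment; this is why the text asks rather than requires.

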8.3 Lost to Follow-Up

When a subject misses a required treatment session, there is a 3-day grace period during which subjects can access treatment from the app. During this time, subject will receive email and text message reminders to complete treatment. Similarly, subjects that miss a data collection point will be contacted by Curebase via email and phone and in the case of surveys, Curebase will attempt to contact the subject and reschedule the missed data collection as soon as possible. The study physician staff and Curebase will counsel the subject on the importance of maintaining the assigned visit schedule and ascertain whether or not the subject wishes to and/or should continue in the study. Subjects that do not respond to contact attempts and do not complete the minimum number of surveys in phase 3 will be classified as described in the Statistical Analysis Plan.

Study Assessments and Procedures

8.4 Efficacy Assessments

The efficacy of GDH will be established using a set of patient-reported outcomes (PROs). These include PROs to capture:

- Abdominal Pain
- Stool Consistency

The primary endpoint of EASITx is abdominal pain, and as such the most important PRO instrument in the study is the **Abdominal Pain Daily Survey**.

Stool frequency and consistency are secondary endpoints of EASITx, so the second-most important PRO instrument in the study is the **Daily Stool Consistency Diary, which uses the Bristol Stool Scale Form**.

Other PROs are assessed at baseline (Week -4), the final week of Phase 3 (week 16), and via the LTE questionnaires at 6-months post-treatment (week 38) and 12-months post-treatment (week 64). These include:

- IBS Quality of Life
- TIS (measured at baseline only)
- WPAI (also at week 8)
- PHQ-4
- Adequate Relief

The Satisfaction Questions will be asked only during the last week of Phase 3 (week 16).

Certain endpoints will be calculated based on the data input via the PROs. These include:

- Stool frequency
- Pain frequency

During the baseline visit, physicians will obtain questions regarding the subject's medical history; for example, physicians will inquire about prior treatments for IBS and history of taking medications that may conflict with the eligibility criteria for the study. However, no medical records or EMR-originating source documentation will be collected. The IBS diagnosis is established at the baseline visit via Rome IV criteria. There is no imaging or laboratory testing required in the study and all endpoints are obtained via PROs via the Curebase software. All subjects who enroll in EASITx will electronically sign a HIPAA Authorization Form, which permits the use of a pseudonymized form of their data to be used for research purposes.

8.4.1 Daily Abdominal Pain Intensity

The daily pain intensity measurement is recorded at approximately the same time each day and is the worst abdominal pain score for the previous 24-hour period using the 11-point NRS of pain intensity.

8.4.2 Daily Abdominal Pain Frequency

The daily pain frequency measurement is derived from the daily pain intensity measurement. Days where severity is >0 are considered a day with pain and are recorded as positive. Days with a score of 0 are days without pain.

8.4.3 Daily Stool Consistency

The daily stool consistency measurement is based on the Bristol Stool Form Scale (BSFS). The BSFS is a scale with pictures and associated descriptions of stools with different consistency. The stool consistency is designated on the scale as 1 (separate hard lumps) to 7 (watery, no solid pieces) and is recorded at approximately the same time each day by referring to pictures and verbal descriptors in the Curebase ePRO (29).

Subjects will be asked for the number of bowel movements in the previous 24 hours. For days where subjects report ≥ 1 bowel movement they will use the BSFS to score the worst stool in the preceding 24 h period.

8.4.4 Daily Stool Frequency

All subjects will record the daily number of bowel movements for the previous 24-hour period.

8.4.5 IBS-QOL

The IBS-QOL is a 34-item questionnaire (21). The items are summed and transformed to a 0-100-point scale. Higher scores indicate better IBS quality of life. The mean IBS-QOL score measured at weeks 16, 38, and 64 will be used for comparison.

8.4.6 WPAI

The WPAI is a 6-question survey of presenteeism and absenteeism (22). Because it has a recall period of 7 days, it will be measured at the baseline screening visit, week 8, week 16, and again during the LTE at weeks 38 and 64.

8.4.7 TIS

The TIS is a 17-item questionnaire of personal characteristics thought to be related to therapeutic response to clinical hypnosis (23). TIS will be measured at baseline in the pre-treatment run-in period and used to model outcomes at treatment completion.

